#### Data Analysis Plan:

### STATISTICAL METHODS & POWER CALCULATIONS

**Overview.** In all analyses for Aim 1 and Aim 2, primary inference will be drawn based on intention to treat (ITT) analyses. Average complier effect (ACE) will be used to inform the metformin effect under full compliance to treatment assignments (Angrist et al, 1996). Per protocol analyses will be used to inform the metformin effect among completers. All analyses will be carried out unadjusted and with adjustment for covariates (Table 7) and covariate interactions with treatment and time. Corrections for multiple comparisons will be applied as appropriate.

The impact of metformin treatment on the progression of frailty status (non-frail, pre-frail, frail) over time will be assessed with a repeated measures mixed effects multinomial logistic model that models the log-odds of adjacent frailty statuses in terms of an indicator of metformin use, time, and the metformin use by time interaction. The possibility of non-linear trends of the log-odds of frailty statuses will be assessed by including an additional time factor (e.g., time squared) and its interaction with metformin use. The best fitting model will be used for inference. Secondary outcomes including gait speed, 6 minute walk, SPPB, frailty index constructed from the research data collected according to the Rockwood index (Searle et al., 2008; Rockwood et al., 2007), and body composition will similarly assessed. Under the linear trend model, the beneficial impact of metformin will be revealed by a significant time by treatment interaction associated with the log-odds of frailty status progression, indicating that the rate of increase in the likelihood of frailty progression over time is reduced in the metformin arm relative to the placebo arm. Under the non-linear trend model, the impact of metformin will be revealed by a significant reduction in the log-odds of frailty status progression in the metformin arm versus placebo at certain time points during the follow-up. SAS proc **nlmixed** will be used in the mixed effects model analyses. Proc **nlmixed** is preferred over other mixed effects modeling procedures such as GEE because it is valid under missing at random (MAR) assumption, accommodates linear and non-linear modelling, and uses maximum likelihood estimation.

Table 7. Covariates included in statistical analyses

Categories of covariates	Baseline	Time Varying
Demographics (age, sex)	X	
BMI (obesity), sarcopenia	X	X

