**3.D.4. Aim 2.** To address the question as to whether an anti-frailty effect of metformin is mediated by its insulin sensitizing and anti-inflammation effects, we will employ the unified mediation analysis framework by Vanderweele. Insulin sensitivity (Matsuda index derived from the OGTT) will be measured at baseline, 6, 12, 18 and 24 months, and 8 biomarkers of systemic inflammation (IL-6, CRP, TNFa, IL-1RA, TNFs R1 and 2, fibrinogen, and transferrin), insulin sensitivity (clamp) and multiple biomarkers of muscle inflammation and insulin signaling (NF $\kappa$ B and MAPK signaling, and mRNA levels of inflammatory cytokines) will be measured at baseline, 12 months, and 24 months. First, we will conduct separate repeated measures mixed effects linear model analyses to assess the effect of metformin treatment on each insulin sensitivity and inflammation measure. In each of these analyses, the outcome (or its normal transformation) will be modelled in terms of an indicator of metformin treatment, time, the treatment by time interaction, and covariates. The coefficient associated with the treatment by time interaction will inform the effect of metformin on the temporal change of each biomarker. We will then conduct repeated measures mixed effects multinomial logistic model to assess whether the odds of an increase in the frailty score is associated with the change in insulin sensitivity from baseline to 24 months ( $\Delta$ IS), and change in inflammation from baseline to 24 months ( $\Delta$ I) by modelling the log-odds of frailty worsening in terms of metformin treatment, time,  $\Delta$ IS,  $\Delta$ I, (metformin) treatment $\times$ time, and covariates. The treatment $\times$ time $\times$  $\Delta$ IS and treatment $\times$ time $\times$  $\Delta$ I interactions will be explored to assess whether metformin attenuates the effect of  $\Delta$ IS and  $\Delta$ I: this effect will be revealed by a significant coefficient associated with treatment $\times$ time $\times$  $\Delta$ IS or treatment $\times$ time $\times$  $\Delta$ I. If some  $\Delta$ IS and  $\Delta$ I measures are collinear, then we will model the odds of frailty worsening in terms of  $\Delta$ IS and  $\Delta$ I separately. All of these analyses will be initially carried out for a pair of an inflammation biomarker and an insulin sensitivity marker separately. Aim 2 will be verified in principle if (i) metformin is associated with significant increase in  $\Delta$ IS and decrease in  $\Delta$ I; and (ii) frailty worsening is

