
associated with significant decrease in  $\Delta IS$  and increase in  $\Delta I$ ; and (iii) the indirect effects of metformin (mediated by  $\Delta I$  and  $\Delta IS$ ) calculated based on Vanderweele are significant.

**3.D.5. Power Calculation for Aim 2. Inflammation.** A 3 month clinical trial of insulin sensitizers versus placebo in patients with impaired glucose fasting glucose or diabetes found decreased TNF $\alpha$  in treated patients (effect size =1.5) . Assuming the same or larger decrease in TNF $\alpha$ , 60 completers in each group, 6 repeated measures, autocorrelation 0.5, and overall type 1 error of 0.05, we expect to have power  $\geq 95\%$  to detect a group difference with regard to mean TNF $\alpha$  and power  $\geq 95\%$  power to detect an increase in TNF $\alpha$  and frailty worsening in the combined cohort [PASS Version 11, NCSS Kaysville UT 2011]. **Insulin sensitivity.** The Diabetes Prevention Program demonstrated improved fasting glucose in metformin treated adults (decrease of 4.1 mg/dL) with pre-diabetes and increased fasting glucose (by 0.4 mg/dL) in placebo group . Assuming the same treatment effect on fasting glucose in this study, and n=60 completers per arm, this study will attain a power of 80% for testing the null hypotheses of no treatment effect, two sided testing, 6 repeated measures, and an autocorrelation of 0.5 [PASS Version 11, NCSS Kaysville UT 2011].

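### The Aim 2 verification rule does not use the randomised effect of metformin on frailty, so it can declare mediation of an anti-frailty effect that the trial has not shown

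*Combined protocol and SAP*

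**What the plan says.** Section 3.D.4 (Aim 2) poses the question of "whether an anti-frailty effect of metformin is mediated by its insulin sensitizing and anti-inflammation effects". It then gives a complete decision rule with three criteria:

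- (i) "Aim 2 will be verified in principle if (i) metformin is associated with significant increase in" insulin sensitivity, together with a decrease in inflammation;
- (ii) frailty worsening is "associated with significant decrease in" insulin sensitivity, and with an increase in inflammation;
- (iii) "the indirect effects of metformin (mediated by" the marker changes) are significant.

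The supporting frailty model is built "by modelling the log-odds of frailty worsening in terms of metformin treatment, time", the two marker changes, treatment-by-time and covariates. The two markers are put in separate models only if they are collinear. On the choice of markers: "All of these analyses will be initially carried out for a pair of an inflammation biomarker and an insulin sensitivity marker separately". No deciding pair is named.

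The randomised comparison of frailty belongs to Aim 1. In the Overview of the statistical methods, under the linear trend model, "the beneficial impact of metformin will be revealed by a significant time by treatment interaction". Nothing in 3.D.4 makes the Aim 2 conclusion depend on that result.

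**The concern.** Only criterion (i) is protected by randomisation. Criterion (ii) is an association, within the trial, between how a patient's markers changed and how that patient's frailty changed. Illness, inactivity or weight change could drive both. Criterion (iii) is built from the paths behind (i) and (ii), so it inherits the same weakness. Treatment and treatment-by-time are in the frailty model, but the rule uses neither coefficient.

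At stake is a contradictory report. Aim 1 could show no difference in frailty between arms while Aim 2, under its own written rule, is declared verified in answer to a question about a mediated anti-frailty effect.

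**Working it through.** **Inputs from the plan (3.D.5).** 60 completers per arm; two-sided 5% tests; TNF-alpha effect size 1.5 with power of at least 95%; power of 80% for the insulin sensitivity part, using a fasting glucose difference of 4.1 + 0.4 = 4.5 mg/dL; power of at least 95% for the association of TNF-alpha with frailty worsening, with no effect size given.

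**The plan's own figures.** For TNF-alpha the noncentrality is 1.5 × √(60/2) = 8.2, so power exceeds 99.9%, consistent with the stated 95% or more. The 80% figure cannot be checked because no SD is given. On a single measure it implies an SD of about 4.5/0.51 = 8.8 mg/dL. The plan states no error rate for the Aim 2 rule.

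**Marker effects used.** The standardised difference that gives the stated power is d = (1.960 + z_power) × √(2/60). For 80% power, d = (1.960 + 0.842) × 0.183 = 0.51 (0.52 with the t distribution). For 95% power, d = (1.960 + 1.645) × 0.183 = 0.66. The inflammation value is well below the plan's 1.5.

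**Why the rule can be met with no frailty effect.** Let each marker change have within-arm correlation r with frailty change (negative for insulin sensitivity, positive for inflammation), and let the markers correlate −0.3 with each other. Metformin shifts the markers only. With both markers in the model, each has a coefficient of size r/1.3. At r=0.4 this is 0.308. The apparent indirect effect is −0.308 × (0.52 + 0.66) = −0.36 SD, and the fitted direct effect is +0.36 SD. They cancel to the true total of zero, but the rule looks only at the indirect part.

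**Simulation.** 120 patients per trial, 3,000 to 4,000 trials per setting, linear frailty outcome, Sobel test for each indirect effect, no effect of metformin on frailty.

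| r (assumed) | Criteria (i)+(ii), joint model | All three, joint model | All three, one marker per model |
|---|---|---|---|
| 0 | about 0% | about 0% | about 0% |
| 0.2 | 7% | 2% | 14% |
| 0.3 | 37% | 17% | 44% |
| 0.4 | 69% | 50% | 68% |
| 0.5 | 76% | 70% | 74% |

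The joint model is the plan's default, so the third column is the relevant one.

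**Sensitivity to the set-up.** With marker effects of 1.5 and 0.8 SD and one marker per model, the rule is met in 78% of trials at r=0.3 and 97% at r=0.4. A binary outcome lowers the rates. In a second set of runs (1.5 and 0.51 SD, one shared cause, joint model, Monte Carlo intervals for the indirect effects), r=0.3, 0.4 and 0.5 gave 37%, 60% and 72% with a frailty score, against 14%, 29% and 42% with binary worsening at 52.5%, the midpoint of the projected 47–58%.

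**A rough anchor for r.** By Fisher's transformation, 95% power for a correlation in 120 patients needs z = (1.960 + 1.645)/√117 = 0.333, that is r of about 0.32. This concerns TNF-alpha only and does not say how much of the association would be non-causal.

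**Effect of requiring a significant frailty benefit.**

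- No effect on frailty: the rule is met in at most about 3.5% of trials in every setting run.
- A purely direct benefit of 0.8 SD, markers linked to frailty only by a shared cause: mediation is still declared in about 18%, 51% and 68% of trials at r=0.3, 0.4 and 0.5, much as without the requirement.
- A truly mediated effect: correct verification falls from 16% to 6% at r=0.3 and from 50% to 31% at r=0.4.

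**The case against.** The strongest reply is that the question in 3.D.4 presupposes the effect tested in Aim 1. Aim 1 will be reported in any case, Aim 2 as titled asks only whether metformin changes the markers, and the rule is hedged as holding in principle within a self-described pilot. This softens the point but does not remove it. The rule is stated in full, it is attached to the mediation question, and no sentence says what to conclude when Aim 1 shows nothing.

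Three further objections stand and limit the point.

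- **The rates depend on r.** It must be a non-causal, change-on-change correlation that remains after covariate adjustment. The associations in the background mostly concern marker levels, often cross-sectionally. The simulation also leaves out the Table 7 covariates and the planned multiplicity corrections, and it simplifies the ordinal mixed model. In the other direction, choosing among several marker pairs would raise the rates; that was not simulated.
- **A significant indirect effect with a null total effect is not always an error.** If a real indirect benefit is cancelled by an opposing direct effect, mediation through the markers exists. What the trial could not then claim is a net anti-frailty effect.
- **A total-effect condition has a price and is incomplete**, as the last three results above show. Aim 1 has 86% power for an odds ratio of 0.20 (3.D.3), whereas the preliminary data in veterans gave 0.66.

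**Conclusion.** The point holds as a fault in the decision rule. As written, 3.D.4 can declare Aim 2 verified when frailty is the same in both arms, because the randomised frailty effect is not part of the rule and two of its three criteria depend on a non-randomised association. In the plan's default joint model with all three criteria, the rate is about 0% with no residual association, 2% at r=0.2, 17% at r=0.3, 50% at r=0.4 and 70% at r=0.5. These figures assume 60 completers per arm, marker effects of 0.52 and 0.66 SD, a linear outcome and an entirely non-causal r of equal size for both markers.

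A reader might infer that the rule would usually give a false answer. The documents do not support that. They give no strength of confounding, and the default model passes one half only above r of about 0.4. Higher rates at smaller r come from one-marker models, larger marker effects or dropping criterion (iii). A reader might also infer that a significance gate on Aim 1 would make the mediation claim safe. It would not, because it leaves confounded mediation untouched when metformin acts on frailty directly. The structural fault itself does not depend on r.

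**What to change.** Amend 3.D.4 before unblinded analysis, as follows:

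1. Report the total (intention-to-treat), direct and indirect effects on frailty together, with intervals. The planned mediation framework already yields all three.
2. State that an anti-frailty effect of metformin is mediated only when the Aim 1 intention-to-treat comparison shows a benefit, with the criterion for benefit fixed in advance. Otherwise conclude only that metformin changed the markers and that marker change was associated with frailty, and report the indirect effect as exploratory.
3. Add a sensitivity analysis for unmeasured marker–frailty confounding, showing how strong it would have to be to remove the indirect effect. 3.D.4 specifies none, and item 2 does not replace it.

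The cost is a few sentences and one extra analysis, with no new data. The real downside is that a full mediation claim becomes limited by the power of Aim 1. The indirect-effect estimate is still reported, so no information is lost.

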**Role of Diabetes in Frailty:** Several studies have demonstrated a strong association between diabetes and frailty. Blaum et al. (2005) found in a study of 599 community-dwelling women that diabetes was significantly associated with pre-frailty (odds ratio [OR] = 2.56, 95% CI: 1.38-4.78) and frailty (OR = 3.92, 95% CI: 1.49-10.34) (Blaum et al., 2005). Kalyani et al. found that post glucose load serum glucose levels were higher in frail compared to non-frail subjects (Kalyani et al., 2012). This group also found that mean oral glucose tolerance test glucose levels were higher at 60, 120, and 180 minutes in frail compared to non-frail older adults (Kalyani et al., 2012). Woods et al. (2005) found that diabetes was predictive of incident frailty, with diabetics having 40% increased risk of becoming frail over the follow-up period (OR = 1.40, 95% CI: 1.11-1.76) (Woods et al., 2005). We have demonstrated that diabetes is predictive of onset of any one of the five frailty characteristics from baseline to follow-up in the SALSA cohort ([name] et al., 2012). In line with these findings, insulin resistance is emerging as an important factor in frailty development. For example, Barzilay et al. (2007) found that insulin resistance was associated with incident frailty (OR = 1.15, 95% CI: 1.02-1.31) (Barzilay et al., 2007). Similarly, Kalyani et al. (2010) recently found that elevated hemoglobin A1c (HbA1c) level was associated with lower scores in the Short Physical Performance Battery (SPPB) which includes gait speed, chair rise, and tandem stand (Kalyani et al., 2010). This group found that category of HbA1c (<5.5%, 5.5-5.9%, 6.0-6.4%, 6.5-7.9%, and  $>8.0\%$ ) was significantly associated with increased probability of developing walking difficulty (P=.049) and reduced lower extremity function (P=.001). HbA1c over 8% (compared to <5.5%) was significantly associated with incident frailty (Hazard Ratio [HR] = 3.33, 95% confidence interval [CI] = 1.24-8.93) and with development of slow walking speed, a component of frailty (HR=2.82, 95% CI: 1.19-6.71). Therefore, both insulin resistance and diabetes are associated with frailty and predict its onset.

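### Section 3.D.5 claims at least 95% power to link TNF-alpha to frailty worsening, but the only effect it assumes is a treatment effect on TNF-alpha, which does not determine that power

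*Combined protocol and SAP*

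**What the plan says.** The inflammation paragraph of section 3.D.5 (Power Calculation for Aim 2) takes its effect from a 3-month trial of insulin sensitizers, which found lower TNF-alpha "in treated patients (effect size =1.5"). It assumes a decrease at least that large, with "60 completers in each group, 6 repeated measures, autocorrelation 0.5, and overall type 1 error of 0.05". From this it states power of at least 95% twice. The first statement is for the group difference in mean TNF-alpha. The second is "power to detect an increase in TNF"-alpha "and frailty worsening in the combined cohort [PASS Version 11, NCSS Kaysville UT 2011"].

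The paragraph gives no odds ratio, correlation or slope between TNF-alpha and frailty.

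Section 3.D.4 describes the analysis of that link: a repeated measures mixed effects multinomial logistic model, "by modelling the log-odds of frailty worsening in terms of metformin treatment, time", the changes in insulin sensitivity and inflammation, treatment by time, and covariates. The link is criterion (ii) of the three that Aim 2 must meet. Criterion (iii), the indirect effect of metformin, also depends on it.

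**The concern.** The two power statements concern different quantities. How far metformin moves TNF-alpha is one. Whether people whose TNF-alpha rises more are also more likely to worsen in frailty, given their treatment, is another. Only the first has an effect size.

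With treatment in the model, the 1.5 shift between arms is largely absorbed by the treatment term. What remains to estimate the association is mainly the spread of TNF-alpha change within each arm. A shift of 1.5 is compatible with a strong association there, a weak one, or none.

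At stake is the reading of a null result. A reader told that power is at least 95% would take a non-significant association as strong evidence against the inflammation pathway. The text does not show that the study could carry that conclusion for a moderate association.

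**Working it through.** **Inputs from the documents.** Section 3.D.5: standardised difference 1.5, 60 completers per arm, autocorrelation 0.5, overall type 1 error 0.05. Sidedness is not stated for inflammation. I assume two-sided, as in the insulin sensitivity sentence that follows ("two sided testing, 6 repeated measures, and an autocorrelation of 0.5"). Research Design and Methods: 47-58% expected to worsen in frailty. For the simulation only, treatment odds ratios on frailty of 0.20 (section 3.D.3) and 0.66 (the preliminary data in older Veterans).

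**Input the documents do not give.** The association of TNF-alpha change with frailty worsening, given treatment. A range is assumed below.

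**Step 1: the first 95% claim.** With a single measure, the standard error of the standardised difference is √(2/60) = 0.183, and 1.5/0.183 = 8.2. Power is Φ(8.2 − 1.96), above 99.9%. It stays above 99.9% with 3, 5 or 6 measures, and under compound symmetry or AR(1) at 0.5. This claim is sound on its inputs.

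**Step 2: what 1.5 implies for the second claim.** With equal arms, the correlation of treatment with TNF-alpha is 1.5/√(1.5² + 4) = 1.5/2.5 = 0.60. The variance inflation is 1/(1 − 0.36) = 1.56, equivalent to 120 × 0.64 ≈ 77 subjects. So the effect size fixes the overlap between TNF-alpha and treatment. It does not fix the association within arms, and the second figure cannot be reproduced from the stated inputs.

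**Step 3: Wald approximation.** One binary end-of-study outcome, treatment the only covariate, odds ratio per within-arm SD, N = 120:

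power ≈ Φ( ln(OR) × √(N p(1 − p)) − 1.96 )

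- p = 0.47: √(120 × 0.47 × 0.53) = 5.47. For 95% power, OR = exp((1.96 + 1.645)/5.47) = 1.93. For 80%, exp((1.96 + 0.842)/5.47) = 1.67.
- p = 0.58: √(120 × 0.58 × 0.42) = 5.41. For 95% power, OR = 1.95. For 80%, 1.68.

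**Step 4: simulation.** 60 per arm, arms 1.5 within-arm SD apart on TNF-alpha, 58% worsening on placebo, logistic model with treatment and TNF-alpha. Power for TNF-alpha:

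| Within-arm OR per SD | Treatment OR 0.20 | Treatment OR 0.66 |
|---|---|---|
| 1.0 | 5% | 5% |
| 1.3 | 23% | 28% |
| 1.5 | 48% | 56% |
| 2.0 | 91% | 94% |

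With 47% worsening on placebo and treatment OR 0.20, power is 47% at OR 1.5 and 88% at OR 2.0. Simulated power is somewhat below the Wald figures (59-60% at OR 1.5), partly because a treatment effect lowers the treated arm's worsening rate. The 1.9-1.95 needed for 95% is therefore slightly optimistic.

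**Step 5: leaving treatment out.** With no within-arm association at all and 58% worsening on placebo, TNF-alpha is significant in 70% of runs at treatment OR 0.20 and in 10% at 0.66. Neither reaches 95%, and the 70% only restates that treatment moves both variables.

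**The case against.** The sentence is garbled and the PASS inputs are not shown, so an unreported association effect may lie behind the figure. The sentence could also mean a pooled comparison of TNF-alpha between worseners and non-worseners. With 56-70 worseners among 120, 95% power then needs a standardised difference of only about 0.66, and 1.5 gives over 99.9%. This is a fair reading of "frailty worsening in the combined cohort". But it uses a treatment contrast as if it were a contrast between worseners and non-worseners, which the text does not justify, and it is not the model in section 3.D.4. What stands is that a reader might infer that 1.5 says nothing about the association, or could never yield the figure. Both are too strong: the effect size fixes the overlap with treatment, and an unstated assumption may exist.

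A reader might also infer that the study is badly underpowered here, for example from "insulin resistance was associated with incident frailty (OR = 1.15, 95% CI: 1.02-1.31"). That figure concerns insulin resistance, not TNF-alpha, and has no stated unit, so it cannot be placed on a per-SD scale. The protocol's Table 4 points the other way. For example, the standardised difference in fibrinogen between pre-frail and frail is (70.4 − 51.2)/18.98 ≈ 1.01, with 18.98 the pooled SD, or roughly an odds ratio of 2.75 per SD if normality and equal variances are assumed. Those are cross-sectional levels of other markers, so they do not supply the missing input either.

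Repeated frailty outcomes would raise power above the figures shown. The gain depends on the within-person correlation: the 0.5 in section 3.D.5 is for TNF-alpha, and none is given for frailty. Finally, this is a pilot, TNF-alpha is one of several markers, and neither enrolment nor the Aim 1 power calculation is affected. That limits the consequence but does not make the figure supported.

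**Conclusion.** The point holds in a bounded form. The first 95% claim in section 3.D.5 is supported. The second does not follow from the only effect assumed, because the planned model includes treatment and no within-arm association is stated. With the difference of 1.5 held fixed, adjusted power in the simplified model runs from 5% with no within-arm association to about 88-94% at an odds ratio of 2.0 per SD, so the stated input does not settle the answer.

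The illustrative sizes rest on the one-outcome logistic model with treatment as the only covariate. They are not the power of the planned mixed multinomial analysis, which could be higher with repeated outcomes, or lower with further covariates that are correlated with TNF-alpha. The documents do not show that true power is below 95%; they show that the 95% lacks a stated basis.

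**What to change.** Withdraw the second 95% figure. Alternatively, replace it with the power, or the detectable odds ratio, computed for the section 3.D.4 model with treatment included, and state:

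- the assumed association per SD of TNF-alpha change, given treatment, and its source;
- the assumed within-person correlation of the frailty outcome and the number of outcomes per person;
- the sidedness of the test.

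If a simplified calculation such as the one above is used instead, it should be labelled as an approximation. The first 95% statement can stay.

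Withdrawal costs one sentence. Replacement needs a short simulation of the planned model. Neither changes the design, the sample size or the analysis. The downside is that the stated figure becomes less favourable.

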Based on our work and others, we project that 47-58% ( $n =56-70$ ) will worsen in frailty status over the period of the study ([name] et al., 2012; Gill et al., 2006). This is likely an under-estimate given the fact that all subjects in this study will be pre-diabetic and will be at increased risk for developing diabetes as compared to this prior work.

Aim 2. The goal of this Aim is to gain insight into the mechanism(s) underlying the effect of metformin on frailty. In Aim 2 we will test two potential mechanisms:

(1) A reduction in insulin resistance (i.e., increased insulin sensitivity). Because metformin is an insulin sensitizer used to treat type-2 diabetes, metformin could reduce/delay the development of frailty through its action on the natural course of diabetes development.

(2) A reduction in chronic inflammation. As noted above, increased inflammation is believed to be fundamental in the etiology of frailty. Because metformin has been reported to reduce inflammation in subjects with diabetes (Carter et al., 2005), metformin could reduce/delay the development of frailty by reducing the inflammation in pre-diabetic subjects.

To test these two potential mechanisms we will measure:

- 1) insulin sensitivity at baseline, at year 1, and year 2 (at the end of the study). However, if a participant converts to diabetes based on the oral glucose tolerance test which will be conducted every 6 months, insulin sensitivity will be measured immediately without waiting until the 1 or 2 year time point
- 2) markers of tissue inflammation (muscle) at baseline, year 1, and year 2 (end of the study)
- 3) markers of systemic inflammation (plasma) at baseline and every 6 months thereafter during the two years of treatment with metformin (or placebo)

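### The 80% power that section 3.D.5 labels insulin sensitivity is a fasting-glucose calculation on six measures; no power is given for the clamp or the Matsuda index

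*Combined protocol and SAP*

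**What the plan says.** Section 3.D.5 (Power Calculation for Aim 2) has a part labelled insulin sensitivity. Its only effect comes from an earlier diabetes prevention trial: "improved fasting glucose in metformin treated adults (decrease of 4.1 mg/dL) with pre-diabetes" and "increased fasting glucose (by 0.4 mg/dL) in placebo group". It then says "Assuming the same treatment effect on fasting glucose in this study, and n=60 completers per arm, this study will attain a power of 80" per cent, with "two sided testing, 6 repeated measures, and an autocorrelation of 0.5". It gives no SD and no alpha of its own.

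Section 3.D.4 (Aim 2) names two insulin-sensitivity measures. For the first it says "Insulin sensitivity (Matsuda index derived from the OGTT) will be measured at baseline, 6, 12, 18 and 24 months", which is five time points. The second is the clamp, at baseline, 12 and 24 months. The Aim 2 text under Research Design and Methods agrees on the clamp: "insulin sensitivity at baseline, at year 1, and year 2 (at the end of the study", with an extra clamp if a participant converts to diabetes. It names the clamp as the method for quantifying insulin sensitivity. Table 7 lists fasting glucose as an item separate from the Matsuda index and the clamp.

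Section 3.D.4 tests each measure by the treatment-by-time interaction in a mixed linear model. Aim 2 counts as verified only if, among other conditions, metformin significantly increases the change in insulin sensitivity from baseline to 24 months.

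**The concern.** A power figure is useful only for the endpoint and test it was computed for. Here the label names one endpoint and the calculation uses another. Fasting glucose is related to insulin sensitivity, but the plan itself does not count it as an insulin-sensitivity measure. No other power statement covers the clamp or the Matsuda index.

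The visit count adds to the doubt. Six is not the number of clamps, Matsuda values or fasting glucose values. It does equal the number of frailty assessments in the visit table (screening, 3, 6, 12, 18 and 24 months) and the number of measures in the Aim 1 simulation. That suggests it was carried over from Aim 1, but does not prove it.

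What is at stake is the reading of Aim 2's first condition. A reader who takes the 80% at face value could treat a null clamp result as evidence against the mechanism, although the plan never established its power to detect an effect on the clamp.

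**Working it through.** **1. Inputs.** From 3.D.5: arm difference 4.1 + 0.4 = 4.5 mg/dL in fasting glucose, "n=60 completers per arm", two-sided testing, 6 measures, autocorrelation 0.5. Assumed: alpha 0.05, taken from the adjacent TNF-alpha calculation.

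**2. Visit counts.**

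| Measure | Schedule | Count |
|---|---|---|
| Clamp | baseline, 12, 24 months | 3 |
| Matsuda index | baseline, 6, 12, 18, 24 months | 5 |
| Fasting glucose | every 3 months over 24 months, plus baseline | 9 (5 if taken only from the OGTT) |
| Used in 3.D.5 | | 6 |

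**3. Trying to reproduce the 80%.** For a comparison of arm means over m visits, power = Φ(4.5 / (SD × √(2v/60)) − 1.96). Here v is the variance factor of the mean of m correlated measures:
- equal correlation: v = (1 + (m − 1) × 0.5)/m
- AR(1): v = [m + 2Σ(m − k) × 0.5^k]/m²

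At m = 6, v = 3.5/6 = 0.583 (equal correlation) or 14.0625/36 = 0.391 (AR(1)). The SD is missing, so the 80% cannot be reproduced. Solving backwards, SD = 4.5 / (2.802 × √(2v/60)), which is 11.5 mg/dL under equal correlation or 14.1 mg/dL under AR(1). Neither figure is in the documents. If the SD is assumed to lie between 8 and 16 mg/dL, power at six measures runs from 98% down to 52% (equal correlation) or from 99.9% down to 69% (AR(1)).

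**4. Clamp and Matsuda index.** The documents give no treatment effect and no SD for either, so their power cannot be computed.

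**5. Illustration of the visit count alone.** Keep the standardised effect that gives 80% at m = 6 and change only m: power = Φ(2.802 × √(v6/vm) − 1.96). I used three correlation structures:
- Equal correlation: v5 = 3/5 = 0.600; v3 = 2/3 = 0.667.
- AR(1), 0.5 between successive visits whatever their spacing: v5 = [5 + 2(2 + 0.75 + 0.25 + 0.0625)]/25 = 0.445; v3 = [3 + 2(1 + 0.25)]/9 = 0.611.
- AR(1) tied to elapsed time: six visits over 24 months are 24/5 = 4.8 months apart, so 0.5 applies per 4.8 months. Visits 6 months apart (1.25 units) correlate 0.5^1.25 = 0.420; 12 months (2.5 units), 0.5^2.5 = 0.177; 18 months (3.75 units), 0.5^3.75 = 0.074; 24 months (5 units), 0.5^5 = 0.031. Then v5 = [5 + 2(4 × 0.420 + 3 × 0.177 + 2 × 0.074 + 0.031)]/25 = 0.391, and v3 = [3 + 2(2 × 0.177 + 0.031)]/9 = 0.419.

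| Structure | v6 | Power at 5 measures | Power at 3 measures |
|---|---|---|---|
| Equal correlation | 0.583 | 78.9% | 74.6% |
| AR(1) by visit | 0.391 | 74.7% | 61.0% |
| AR(1) by elapsed time | 0.391 | 79.9% | 77.2% |

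Example for three measures under AR(1) by visit: 2.802 × √(0.391/0.611) = 2.240; 2.240 − 1.960 = 0.280; Φ(0.280) = 0.610.

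**6. TNF-alpha.** The same section also uses 6 measures for TNF-alpha. The Aim 2 design text and the follow-up schedule put plasma markers at every 6 months (5 times with baseline). Section 3.D.4 puts them at baseline, 12 and 24 months (3 times). If the stated effect size of 1.5 is a standardised difference, even one measure gives 1.5 × √(60/2) − 1.96 = 6.26, which is power above 99%. The group-difference claim of at least 95% does not depend on the count.

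**The case against.** The 3.D.5 sentence says openly that it assumes an effect on fasting glucose, so the substitution is disclosed and only the label misleads. This is a pilot, Aim 2 is mechanistic, and the sample size does not rest on this figure. No arithmetic error is shown, because without an SD the 80% can be neither confirmed nor refuted. All of that is fair, and it limits the point to a mislabelled endpoint with missing inputs. It does not supply a power for the clamp or the Matsuda index.

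A reader might go further and infer that the true power for the clamp is 61%, or at least below 80%. The documents do not support that, for three reasons:
- The table carries a fasting-glucose effect over to a different measurement. At three measures, a clamp standardised effect larger by √(0.667/0.583) − 1 = 7% (equal correlation) or √(0.611/0.391) − 1 = 25% (AR(1) by visit) restores 80%. The direction of the error is unknown.
- The lowest figures treat clamps 12 months apart as correlating like visits about 5 months apart. Tying correlation to elapsed time removes most of the loss.
- The illustration compares arm means over all visits, whereas the planned test is treatment by time.

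Counting only post-baseline clamps (two measures) gives lower figures still, 69.5% or 52.5%. That is not like for like if the reference six includes baseline.

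**Conclusion.** The point holds as a mismatch between label, endpoint and visit count. The 80% in 3.D.5 is a fasting-glucose figure with an unstated SD. It is not the power for the clamp or the Matsuda index, and six measures fits neither of those schedules nor that of fasting glucose. The endpoint mismatch is the main defect and rests on the plan's wording alone.

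The count mismatch is secondary. On a carried-over standardised effect, an arm-mean comparison, 60 per arm and alpha 0.05, it costs from almost nothing to about 5 points at five measures, and about 3 to 19 points at three. These sizes are illustrative. The actual power for insulin sensitivity is unknown and could lie on either side of 80%. Because the planned test is an interaction, the 80% may not apply to that test even for fasting glucose.

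**What to change.** - Relabel the 80% as power for fasting glucose only. State its SD, its alpha, the contrast tested and the actual number of measures.
- For the clamp and the Matsuda index, state an expected difference and SD with their source. Recompute power at 3 and 5 visits for the planned treatment-by-time contrast (change to 24 months). If no effect can be supported, say that no power is claimed for them.
- For TNF-alpha, first reconcile the two plasma-marker schedules, then change the count of 6 to match. Simply writing 5 would pick one side of an unresolved conflict. The group-difference power of at least 95% is unaffected.

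The cost is a short recalculation and a narrower power claim for Aim 2. No patients or visits are added.
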